#### iv. Control or comparison group use

Controls will be children from the same patient population as those receiving AA-ORS. These children will receive a placebo solution containing all the non-amino acid and non-electrolyte components of the AA-ORS and therefore will be able to contribute useful information regarding the feasible dose of the solution. This placebo solution is produced by the manufacturer of the AA-ORS for the purpose of clinical studies. Because these children will not be receiving the amino acids, they will provide the background rate of AEs (and morbidity experience) of children in this population, allowing for the detection of an unusually high event rate in the AA-ORS group, should it arise.

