#### ii. Aims of proposed research study

We propose to conduct a small pediatric pilot study to determine patient safety, feasible product volume (trends in dosage consumed over 14 days, etc.), and caregiver (i.e., parent or legally acceptable representative) acceptability of AA-ORS in the target population at risk for EED. To assess the product's safety, we will randomize children to receive active product or placebo and compare the rate of adverse events (AEs) in the two groups. We will also assess the extent to which the product might meet the needs of the target population and setting. Results from this study will be used to inform:

- a) The design of a randomized controlled trial to test the efficacy of AA-ORS for treating pediatric EED.
- b) Future EED product development efforts.
- c) Program implementation strategies for EED interventions.

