#### Endpoints

**Primary:** Adverse events and serious adverse events through 21 days of follow-up, and changes to dietary and digestive habits through day 14 of follow-up.

**Primary:** Average product volume consumed daily through 14 days of follow-up, time trends in average daily volume consumed, and factors that influence children’s willingness and ability to ingest the product as intended.

**Secondary:** Key factors that influence caregiver willingness to have the product used by their children, and their perception of their child’s response to its consumption.

**Exploratory:** Average plasma/serum concentrations of metabolic, gut dysfunction, systemic inflammation, and micronutrient biomarkers at baseline and day 15 of follow-up.

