### *Sampling Strategy*

Estimated sample size: We expect to enroll 132 participants, which includes 66 caregivers, and 66 children (aged 12–24 months); half of these child-caregiver pairs will be randomized to receive AA-ORS (n= 33) and half to receive placebo solution (n= 33). We anticipate that there will be a dropout rate not to exceed 10%. We have incorporated this expected withdrawal rate into the final sample size numbers.

For the primary endpoint of safety in this study, 30 subjects in each arm would result in more than 95% probability of observing at least one AE if the rate of that type of event in the subject population after being exposed to AA-ORS is 10%. To have a 95% probability of being able to detect at least one AE if the rate of that event is truly 5%, the sample size would have to be at least 60 per arm. For more

rare events, the sample size would have to be much larger. Table 6 below shows the probabilities of observing an event with various sample sizes and varying true rates of that event in the population.

**Table 6.** Probability (P) of observing none, one, or more adverse events (AEs) at different true rates of AEs in the population.

N (per arm)	Rate of AE	P of 0 AEs	P of 1+ AEs	P of 2+ AEs	P of 3+ AEs
20	0.15	3.9%	96.1%	82.4%	59.5%
	0.2	1.2%	98.8%	93.1%	79.4%
30	0.1	4.2%	95.8%	81.6%	58.9%
	0.15	0.8%	99.2%	95.2%	84.9%
40	0.1	1.5%	98.5%	92.0%	77.7%
	0.15	0.2%	99.9%	98.8%	95.1%
50	0.1	0.5%	99.5%	96.6%	88.8%
	0.15	0.03%	99.97%	99.7%	98.6%
60	0.05	4.6%	95.4%	80.8%	58.3%
	0.1	0.2%	99.8%	98.6%	94.7%

Gray highlighted cells are those with a probability of 95% or higher. Blue highlighted cells are those representing a true AE rate of 0.1 or lower.

Increasing the per-arm sample size above 30 (but < 60) does not add much in terms of increasing the probability of detecting an AE with a true rate in the population of 10%. However, 30 subjects per arm has relatively low power for an efficacy endpoint using biomarkers. For example, a sample size of 30 per arm provides approximately 80% power for a t test to detect a 376 ng/ml (21.9% reduction) difference in soluble CD14 (marker of bacterial translocation) between the arms assuming the mean sCD14 is 1,715 ng/ml in the placebo group. These calculations used data from an infant cohort in Zimbabwe (23) (SD = 520 ng/ml).

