**STUDY ENDPOINTS TO BE ANALYZED AND ANALYTICAL METHODOLOGY**

**Primary:** AEs and SAEs through 21 days of follow-up, and changes to dietary and digestive habits through day 14 of follow-up.

*For AEs and SAEs that occur within 21 days of enrollment, statistical comparisons will be made between the AA-ORS and the placebo solution groups using Fisher's exact test. Changes to feeding habits (normal, less frequent/less volume, more frequent/more volume), diarrhea (1–2, 3–4, 5–7, or 7+ events in 24 hours), and vomiting (none, 1, 2–5, > 6 events in 24 hours, or hospitalization) will be made using chi-square tests.*

**Primary:** Average daily product volume consumed through 14 days of follow-up, time trends in daily volume consumed, and factors that influence children's willingness and ability to ingest the product as intended.

*The average daily volume (and statistical distribution) of solution consumed by children over the 2-week period will be calculated. These descriptive data will be pooled from AA-ORS and placebo arms as the solutions are designed to taste the same. Lowess curves will be used to describe trends in volumes consumed, and linear mixed effects models will be used to test for an association between day of follow-up and product volume consumed. We will use linear regression to identify factors (e.g., child weight, length, and age) associated with a child's average daily intake.*

**Secondary:** Key factors that influence caregivers' willingness to have the product used by their children, and their perception of their children's response to its consumption.

*These qualitative analyses will use ATLAS.ti software to identify and group key themes and topics from IDI notes.*

**Exploratory:** Average plasma/serum concentrations of metabolic, gut dysfunction, systemic inflammation, and micronutrient biomarkers at baseline and day 15 of follow-up.

*Metabolic, EED, systemic inflammation, and micronutrient marker data collected at baseline will be pooled across intervention groups and used to generate descriptive statistics for the study population. The same descriptive statistics will be generated for day 15 of follow-up. Paired student's t test will be used to compare these continuous parameters between baseline and day 15 of follow-up.*

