### i. Risks to research study participants/groups

#### *Risk Considerations*

The proposed study is expected to be of minimal risk as the study AA-ORS is a medical food product regulated by the US FDA. As a result, we do not anticipate any adverse events for this study related to the administration of AA-ORS, but we will include a control arm in order to better assess the safety of this product in children with mild-moderate stunting. Children with mild to moderate stunting are at increased risk for morbidity and mortality, so we anticipate that participants may report diarrhea or respiratory infections at high rates, regardless of receipt of active AA-ORS or placebo. While there is mounting evidence that microbiome immaturity contributes to growth deficits in LRS, any changes to the microbiome composition and diversity from provision of AA-ORS are likely to be transient, based upon previous observations among infants and children provided probiotic-supplemented formula or ready-to-use supplementary food (43, 44).

This study involves blood specimen collection. The collection of these samples involves venipuncture, which may cause discomfort, pain, introduction of infection, bleeding, fainting, or bruising. Precautions will be taken to avoid introduction of infection by disinfecting the site of venipuncture and using sterile equipment. The risk of bleeding and bruising will be minimized by immediate application of pressure after venipuncture. The child will be restrained appropriately by the caregiver to prevent kicking of the phlebotomist. A thorough description of potential risk considerations and mitigation strategies is outlined in Table 7.

**Table 7.** Known risks and mitigation strategies for SAFE study participants.

Potential risk to participant	Concern	Study design feature intended to minimize risk	Rationale for the necessity of exposing participants to risk

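### The primary safety comparison plans significance tests without an effect estimate or interval, at a size that can detect only a large excess of adverse events on AA-ORS

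*Combined protocol and SAP*

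**What the plan says.** Safety is the first primary objective. Section C.ii says the investigators will randomize children and "compare the rate of adverse events (AEs) in the two groups". The endpoint is "Adverse events and serious adverse events through 21 days of follow-up", together with changes in dietary and digestive habits to day 14.

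Section C.iv gives the reason for a placebo arm: it shows the background rate of events, "allowing for the detection of an unusually high event rate in the AA-ORS group, should it arise".

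The sizing argument (Section C.iii, Sampling Strategy) is of a different kind. It says that "30 subjects in each arm would result in more than 95% probability of observing at least one AE" when the true rate on AA-ORS is 10%, and Table 6 tabulates that probability by arm size and rate. Enrollment is 33 per arm, with dropout expected to be no more than 10%. No placebo rate, between-arm difference or power for the AE comparison is given.

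For analysis (Section C.xi), "statistical comparisons will be made between the AA-ORS and the placebo solution groups using Fisher's exact test". Comparisons of feeding, diarrhea and vomiting categories "will be made using chi-square tests". Neither sentence names an effect measure or an interval.

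On background illness, Section D.i says "we anticipate that participants may report diarrhea or respiratory infections at high rates, regardless of receipt of active AA-ORS or placebo".

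**The concern.** Seeing at least one event in an arm and finding a higher rate than placebo are different properties. Only the first was used to choose the size, while Section C.iv claims the second. Where background illness is common, the first property is nearly uninformative about harm. If the background rate of an event is 10%, a product that adds no risk yields at least one such event in 30 children with the same probability as the one quoted for sizing.

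The plan then reduces the between-arm comparison to a test result. With small arms the usual outcome is a non-significant p-value, which does not show how large an excess the data still allow. That upper limit is what a reader needs from a pilot meant to describe safety in an age group with almost no prior data. Nothing in the analysis section produces it, and nothing guards against reading non-significance as reassurance.

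**Working it through.** **1. The plan's own figure.** For 30 children and a true rate of 10%, P(no AE) = 0.9^30 = 0.0424, so P(at least one) = 1 − 0.0424 = 95.8%. This matches Table 6, and the other nine rows reproduce as well. The sizing arithmetic is correct. The calculation contains no placebo rate, so it says nothing about an excess.

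**2. Inputs for the between-arm comparison.**
- From the documents: 33 per arm; Fisher's exact test.
- Assumed: two-sided test (sidedness is not stated); alpha 0.05 (stated only in the biomarker paragraph); each child counted once per event type; placebo rates from 0% to 30% (no figure is given).

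**3. Power.** With a events on AA-ORS and b on placebo, power = Σa Σb Bin(a; 33, pA) × Bin(b; 33, pP) × 1[Fisher p(a, b) ≤ 0.05], summed over all 34 × 34 tables. The last column repeats this with 30 per arm, roughly the number left after 10% dropout (33 × 0.9 = 29.7).

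| Placebo | AA-ORS | Power, 33 per arm | Power, 30 per arm |
|---|---|---|---|
| 0% | 10% | 11% | 7% |
| 5% | 15% | 12% | 9% |
| 10% | 20% | 11.5% | 9.6% |
| 10% | 30% | 42% | 37% |
| 20% | 40% | 32% | 30% |
| 30% | 50% | 32% | 26% |

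**4. Excess needed for about 80% power, 33 per arm.**

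| Placebo | AA-ORS rate needed | Excess (points) |
|---|---|---|
| 0% | 23% | 23 |
| 5% | 33% | 28 |
| 10% | 42% | 32 |
| 20% | 55% | 35 |
| 30% | 65% | 35 |

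**5. Sensitivity to the assumptions.** A one-sided 0.05 test at 33 per arm raises power only to 19% for 10% versus 20% and 54% for 10% versus 30%. The Benjamini-Hochberg adjustment planned for related hypotheses can only lower power for a given event type.

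**6. Event counts.** With no placebo events, 5/33 on AA-ORS gives p = 0.053 and 6/33 is the first significant result. With 3 placebo events, 11 are needed on AA-ORS.

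**7. What an interval adds.** Take 10/33 versus 3/33, more than a threefold difference. Fisher's p is 0.061. The risk difference is 0.303 − 0.091 = 0.212. The Wilson limits are 0.174 to 0.473 for AA-ORS and 0.031 to 0.236 for placebo. Newcombe's 95% limits are then:
- lower: 0.212 − √[(0.303 − 0.174)² + (0.236 − 0.091)²] = 0.018
- upper: 0.212 + √[(0.473 − 0.303)² + (0.091 − 0.031)²] = 0.393

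The p-value alone would be read as no significant difference; the interval shows an excess of between 2 and 39 points. The two disagree about zero because Fisher's test is conservative and the interval is not its inversion.

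In a milder case, 10/33 versus 6/33, p = 0.39 and the interval is −9 to +32 points. The result is non-significant yet compatible with a large excess.

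**8. Would a larger trial be the answer?** By the standard two-proportion formula, 80% power needs 199 per arm for 10% versus 20% (219 with continuity correction) and 62 (72) for 10% versus 30%. That is out of proportion for this pilot, so the remedy lies in estimation and wording.

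**The case against.** This is a phase I pilot, and sizing it on the chance of seeing an event is an accepted design choice. Sampling Strategy says openly what the 95% figure means and adds that rarer events would need many more children. Section C.iv speaks of an unusually high rate, and a very large excess would be found with about 80% power. Detection does not rest on Fisher's test alone either: causality is judged case by case, an independent monitor confirms severity and relatedness, and a Data and Safety Monitoring Board (DSMB) that includes a biostatistician reviews interim safety analyses. Study Limitations promises not to draw conclusions beyond the methods. Section C.ii commits to comparing rates, so per-arm rates are arguably within the plan.

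Much of this stands, and it rules out three stronger readings that a reader might infer:
- **That the claim in Section C.iv fails altogether.** It does not; it holds for large excesses.
- **That a non-significant result will be reported as proof of safety.** No section says so. The documents show only that nothing excludes that reading.
- **That the future efficacy trial will be built on such a conclusion.** Section C.ii says only that the results will inform its design, along with product development and implementation.

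What remains is narrower. The caveats about low power (Study Approach, Sampling Strategy, the biomarker paragraph in C.xi and Study Limitations) concern biomarkers or gut health, including diarrhea frequency as a gut-health measure. The remark on rarer events concerns seeing one event. None says that the between-arm AE comparison is weak. The stopping rules cover weight loss and breastfeeding and set no between-arm AE threshold; the DSMB charter is not among the documents, so its content is unknown. Comparing rates does not commit anyone to an interval.

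**Conclusion.** The concern holds in a limited form. The analysis plan names tests and no estimate or interval for the primary safety endpoint, and the size was not chosen for a between-arm excess. With 33 per arm, a doubling from 10% would be detected about one time in nine and a tripling about four times in ten. Power of about 80% needs an excess of roughly 23 to 35 percentage points for placebo rates between 0% and 30%.

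These figures rest on a two-sided 0.05 level and on illustrative placebo rates, since the documents supply neither for this test. A one-sided test does not change the conclusion. The sizing calculation itself contains no error. This is a worthwhile improvement to the primary analysis and its wording, not a flaw that invalidates the trial.

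**What to change.** **Section C.xi, primary safety analysis.** For any AE, each solicited AE and SAEs, report the number and proportion of children affected per arm and the risk difference (AA-ORS minus placebo) with a 95% confidence interval, for example Newcombe's. Make this the main safety summary and keep Fisher's p-value as secondary. State alpha and sidedness. Vomiting and diarrhea are on the solicited list, so they gain an interval by this route.

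**Section C.iv and Study Limitations (C.xii).** State that the between-arm AE comparison can detect only large excesses, with one or two of the figures above and their assumptions, and that a non-significant result is not evidence of equal safety.

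**Cost.** A few lines of text, some extra table columns and slightly more analysis work. No additional children, visits or data are needed. The price is that the stated claim becomes less favourable.

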#### v. Number and age range of research study participants/groups whose data shall be used

Sixty-six children between the ages of 12 and 24 months and their caregivers will be enrolled into the study.

#### vi. Inclusion criteria for each group of research study participants

##### *Inclusion Criteria*

##### Pediatric and caregiver pairs (must meet inclusion criteria for both categories):

###### Child:

1. Is between 12 and 24 months of age.
2. LAZ between  $-1$  and  $-3$  SD.
3. At least one week post routine immunization or vitamin A supplementation visit at the study site.
4. Has a parent or legally acceptable representative willing and able to provide informed consent.
5. No plans for travel outside of the community for the duration of the study.

###### Caregiver of child:

1. Is a parent or legally accepted representative of a child eligible for this study.
2. Is 18 years of age or older.
3. Has a working mobile phone.
4. Is willing and able to provide informed consent.
5. If illiterate—there is at least one literate adult living in the child's household.

#### vii. Exclusion criteria for each group

##### *Exclusion Criteria*

##### Pediatric and caregiver pairs (must meet none of the exclusion criteria for either category):

###### Child:

1. Has any sign of acute illness, including but not limited to fever, cough, and diarrhea.
2. Is wasted (weight for length z-score  $< -2$  or mid-upper arm circumference [MUAC]  $< 12.4$  cm) or has pitting edema.
3. Is exclusively breastfed.

4. Is seeking medical attention at the health facility other than for routine, preventative care (e.g., immunization visit, vitamin supplementation).
5. Has suffered within the prior week from illnesses that might impact nutritional status (e.g., severe diarrhea or pneumonia; vomiting; persistent diarrhea; cleft lip or palate; blindness; tuberculosis; jaundice; renal or cardiac disease; cerebral palsy; known metabolic disorders; and chromosomal disorders, including trisomy 21).
6. Medical history of chronic health condition (i.e., HIV, hepatitis B or C, end stage renal disease, severe liver disease—absence of a diagnosis is sufficient).
7. Participating in any other clinical trials.
8. Recent (prior 2 weeks) use of antibiotics or any other medical treatments (including ORT, but not including vaccines or vitamin/mineral supplementation).
9. Cannot give the necessary biological (blood) sample.

Caregiver:

Reports diarrhea in the household in the prior 7 days.

#### viii. Gender, race, or ethnicity use as variables in participant selection

Not applicable.

#### ix. Time period in which these data shall be collected and/or stored and time frame for entire study

Data will be collected for this study over a 4-month period, and a permanent master set of data will be kept by PATH for at least 5 years post-completion of the funded project, up to indefinitely. All plasma/serum specimens collected at enrollment and post-dosing visits will be stored in Kenya, analyzed, and destroyed within 5 years. We have included language in the consent form to allow for potential future research with the samples and data related to nutrition or infectious diseases.

#### x. Monitoring conduct of the study to ensure participants' safety, confidentiality, and data integrity

##### *Study Monitoring*

PATH investigators will monitor study activities at the health care facilities where DO and IDIs are conducted. An adverse event case report form (CRF) will be used to record any unanticipated adverse events (Appendix 2). On-site independent study monitor (ISM) will be contracted to oversee compliance with safety monitoring and stopping rules. The ISM will conduct safety monitoring visits every two weeks during the first month of the study, and at least once per month for each subsequent month of the study. During monitoring visits, the ISM will review safety data for participants, including all AEs and SAEs. The ISM will confirm the severity and relatedness assessment initially determined for all AEs, assess weight loss and breastfeeding practices in accordance with the study stopping rules, and confirm that all appropriate AE follow-up and SAE reporting procedures have been followed.

PATH will also regularly review study records and logs for quality assurance purposes.

Study participant confidentiality will be respected. Site monitoring visits may be conducted to:

- Verify compliance with human subjects and other research regulations and guidelines, including confidentiality procedures, informed consent process, and regulatory documentation.
- Assess adherence to the study protocol and study-specific procedures manual.

- Confirm the quality and accuracy of information collected at the study site and entered into the study database, including the validation of data reported on data collection forms.
- Inspect the study facility and documentation (e.g., informed consent forms, data collection forms) as well as observe the performance of study procedures. If a monitor is present during consent, participants will be asked their permission to accept or decline the monitor observing.

To minimize protocol deviations, study staff will be thoroughly trained on study conduct, safety, and careful data management. In the event of a protocol deviation, the event will be documented in the corresponding protocol deviation CRF and the study team will notify the co-PIs within 24 hours. Protocol deviations will be reported to the appropriate ethics committees in accordance with their reporting requirements.

Study procedures will begin only after the study has received necessary ethical and regulatory approval(s) from relevant parties and written informed consent from the participants.

The Pharmacy and Poisons Board (PPB) may also inspect the clinical trial site and trial sponsor to ensure that the principles of GCP are being met. In order to demonstrate compliance with the protocol and applicable regulations, the PI and site PI will maintain a Clinical Trial Master File containing relevant documentation to allow effective supervision. At the request of a properly authorized officer of PPB, the site PI shall permit such officer to have access to, copy, and verify any records or reports made by the investigator. The site PI will notify the sponsor within 24 hours following contact by a regulatory authority. The sponsor will provide any needed assistance in responding to regulatory audits or correspondence.

